2 STUDY OBJECTIVES

The overarching questions of our research are:

- 1) What are the mechanistic differences between patients who develop doxorubicin-induced cardiotoxicity and those who do not?
- 2) How do these differences drive cardiotoxicity?
- 3) Why do they drive cardiotoxicity in some patients and not others?
- 4) Can we predict which patients will develop cardiotoxicity before they become symptomatic?

In this pilot study we have identified three key aims, detailed below, that will allow us to generate preliminary data for the purpose of developing large-scale studies which will be focused towards answering these questions.

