3.3 OUTCOME

Our primary outcome for this study is to generate iPSC-derived cardiomyocytes that are reproducible, amenable to experimental analysis, and that recapitulate the phenotype of the donor at the molecular and cellular level. This will not only allow us to begin addressing the research questions set out in this study of being able to better understand chemotherapy-induced cardiotoxicity, but will also enable us to use the technology to investigate other cardiac conditions and congenital defects.

Secondary outcomes include:

- Identifying a doxorubicin-specific signature in the cells derived from our cardiotoxicity subjects
 which signifies a distinct biological process that is absent in the control group. This would allow us
 a potentially significant insight into the mechanistic effects of doxorubicin-induced cardiotoxicity
 at a cellular and molecular level.
- Identifying candidate biomarkers that are of a functional relevance to doxorubicin-induced cardiotoxicity. Novel biomarker discovery could potentially offer an enhanced alternative to the current standard of risk stratification and cardiotoxicity detection in the clinic.
- Obtaining data that will support further investigations into different areas of future research such as the role of candidate biomarkers that could predict anthracycline-induced cardiotoxicity in other cancers and what their relationships are to cumulative drug dosing strategies for example.

These outcomes could eventually enable clinicians to better predict which patients will develop cardiotoxicity and how their care can be more appropriately managed. The research will deepen the understanding of doxorubicin-induced cardiotoxicity for health care professionals and service providers for integrated care. It will also assist in providing a better understanding of the options available for supporting chemotherapy patients at various stages of their care both during and following the completion of their treatment. It has the potential to improve the wellbeing and lives of patients as well as to improve how primary and secondary care services work together. The study will develop high quality data that will be disseminated with researchers, service users and health care professionals to create more effective practices in care.

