3.6 SAMPLING

3.6.1 Size of sample

The maximum sample size for this pilot study at this stage will be 12 participants in total across all experimental groups (Figure 1). When selecting a sample size for this study we considered several factors including the nature of the study (i.e. a pilot study) and the financial feasibility of achieving our research aims at this stage. As this is a pilot study, we want to generate preliminary data that can support further funding applications that build on scientific evidence and eventually allow for larger sample sizes whilst still working realistically within the constraints of the study. Our approach is therefore to focus our efforts on obtaining a carefully planned smaller sample size which adequately represents significant aspects of the wider study population. This sample size is large enough to sufficiently address the primary research aims at the current stage and will provide valuable preliminary data to plan larger subsequent studies which will further address the overarching research questions.

Version 2.21. Date: 1517/095/2022; IRAS:

Page 23 of 44

Formatted: Indent: Left: 0.35 cm

[figure not shown]

Figure 1. Cancer patients with early-onset chronic cardiotoxicity and late-onset chronic cardiotoxicity will be recruited. Non-cardiotoxic patients will be matched to the cardiotoxic patients on tumour type, treatment regime and approximate age. For late-onset chronic cardiotoxic patients, noncardiotoxic patients will be recruited who have previously received the same treatment regime and not developed cardiotoxicity at the same point.

Version 2.21. Date: 1517/095/2022; IRAS:

Page 24 of 44

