6.2.2.7 Mass Spectrometry (MS)

Version 2.24. Date: 1547/095/2022; IRAS:

Page **31** of **44**

To generate quantitative data on the whole proteome of doxorubicin-treated cardiomyocytes, cardiomyocytes from all experimental groups will be subjected to iTRAQ-based MS. To determine whether protein expression is similar between cardiotoxicity and non-cardiotoxicity samples, the data will be subjected to principal component analysis to analyse the variance across the sample sets and identify whether there is a distinction between them based on protein expression. A two-tailed *t* test will be carried out using the R computational environment to determine the statistical significance of differences in protein expression between cardiotoxicity and non-cardiotoxicity samples

To validate the iTRAQ-MS data, we will use Western blot analysis to verify the differential protein expression of a select number of identified proteins. The identity of the target proteins will be confirmed by comparison to a molecular weight marker (for size) and a positive control if possible (for size and signal). A loading control will be used to allow us to normalise the data and compare the expression levels between the target proteins. The data produced will be interpreted using imaging software, such as ImageJ, and a semi-quantitative comparison will be made of the signals generated between protein bands.

Following validation, proteins which are found to have a statistically significant higher or lower level of expression by MS in the control samples will be explored further using computational enrichment analysis to identify functional pathways involved in cardiotoxicity.

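### Section 6.2.2.7 leaves the global question of whether case and control proteomes are similar to a PCA that ignores the case/control label and has no stated criterion

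*Protocol*

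**What the plan says.** Section 6.2.2.7 describes the iTRAQ mass-spectrometry analysis in three steps.

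- **PCA.** Its purpose is stated as: "To determine whether protein expression is similar between cardiotoxicity and non-cardiotoxicity samples, the data will be subjected to principal component analysis". It is also meant "to analyse the variance across the sample sets and identify whether there is a distinction between them based on protein expression". The section gives no number of components, no definition of separation and no margin for similarity.
- **t test.** The next sentence adds a two-tailed t test "to determine the statistical significance of differences in protein expression between cardiotoxicity and non-cardiotoxicity samples". It is not conditional on the PCA.
- **Follow-up.** Selected proteins are checked by Western blot. After that, "proteins which are found to have a statistically significant higher or lower level of expression by MS in the control samples will be explored further" by enrichment analysis.

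On size, section 3.6.1 says: "The maximum sample size for this pilot study at this stage will be 12 participants in total across all experimental groups". No power, effect size or standard deviation is given, because the number rests on the pilot nature of the study and on finance. Section 2 gives the purpose as to "generate preliminary data for the purpose of developing large-scale studies".

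**The concern.** The section gives PCA an inferential task: to say whether two groups are alike. PCA is not built for that. Its leading components show whatever varies most between samples, whether or not that is related to cardiotoxicity.

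The protocol itself names sources of variation unrelated to the label. Lines may be made by Sendai virus or by electroporation, with different gene sets (6.2.2.1, 6.2.2.2). Section 1.3 attributes epigenetic differences seen in some iPSC lines mainly to the reprogramming method. Section 3.5.1 mentions variable reprogramming efficacy. Early-onset and late-onset cases fall in one comparison (Figure 1 legend, 3.6.1).

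If such variation dominates, the groups will overlap on the plot even when many proteins differ. Read literally, 6.2.2.7 would then let the report call the proteomes similar. The data are meant to support larger studies and funding applications, so a false statement of similarity could misdirect them.

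**Working it through.** **No figure to reproduce.** The sample size of 12 has no power derivation, and the PCA has no stated criterion. Everything below except the maximum of 12 is an assumption. The case:control split is not readable (Figure 1 is not shown), so 6:6 is assumed.

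**Step 1: when does a group difference reach the leading components?** Scale each protein to variance 1. Let a fraction f of proteins differ by d SD between two equal groups. The average variance per protein along the group direction is then about f × d²/4. If a share s of the variance lies in three shared donor, line or batch factors, each factor carries about s/3. The group direction tends to show on PC1-PC2 only if f × d²/4 is comparable with s/3 or larger.

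- f = 5%, d = 2, s = 50%: 0.05 × 4/4 = 0.05 against 0.50/3 = 0.17. The label is hidden.
- f = 10%, d = 2, s = 30%: 0.10 × 4/4 = 0.10 against 0.30/3 = 0.10. Comparable.
- f = 20%, d = 1.5, s = 30%: 0.20 × 2.25/4 = 0.11 against 0.10. The label usually shows.

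**Step 2: simulation.** 6 v 6 donors, 3,000 proteins, three shared factors, 300 runs per setting. Separation means that a straight line on PC1-PC2 divides the groups perfectly. This criterion is assumed, since the protocol states none.

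| Proteins shifted | Shift | s = 0 | s = 30% | s = 50% |
|---|---|---|---|---|
| none | – | 3% | 3% | 1% |
| 1% | 1.5 SD | 40% | 2% | 2% |
| 5% | 1 SD | 97% | 4% | 4% |
| 5% | 2 SD | 100% | 29% | 7% |
| 10% | 1.5 SD | 100% | 37% | 12% |
| 10% | 2 SD | 100% | 82% | 32% |
| 20% | 1.5 SD | 100% | 90% | 47% |
| 30% | 1.5 SD | 100% | 99% | 80% |

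PCA thus finds a real difference almost always or almost never, depending on inputs that the protocol does not supply.

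**Step 3: a global test that uses the label.** Take a summary of the per-protein statistics and compare it with its values under relabelling of donors. With 6 v 6 there are C(12,6) = 924 unrestricted relabellings, or 2⁶ = 64 if labels are swapped only within 6 pairs. In a separate simulation with 5% of proteins shifted by 2 SD, detection was:

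| Shared variance | PCA, PC1-PC2 | Permutation, unrestricted | Permutation, within pairs |
|---|---|---|---|
| 20% | 75% | 99% | 91% |
| 50% | 12% | 39% | 29% |

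The permutation test matched or beat PCA in every setting with a true difference. Part of the gap reflects a looser false-positive rate: under no effect PCA separated in about 2% of runs, and the permutation tests rejected in about 4% and 3%. The ordering is stable. The exact levels at 50% shared variance depend on how the shared factors are modelled and should not be relied on.

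**Step 4: limit of within-set permutation.** With pairs, swapping every label gives the same two-sided statistic, so the smallest p is 2/2ᵏ for k complete pairs.

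- k = 6: 2/64 = 0.031.
- k = 5: 2/32 = 0.0625, which cannot reach 0.05.

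**Step 5: can the t test support similarity instead?** With 6 v 6, df = 10 and the noncentrality is d/√(1/6 + 1/6) = d × √3. Unadjusted two-sided power at 0.05 is 0.35 at 1 SD, 0.65 at 1.5 SD and 0.88 at 2 SD. A non-significant protein is therefore no evidence of similarity either.

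**The case against.** **The t test follows directly.** The strongest reply is that differences are tested by a label-based t test in the next sentence, whatever the PCA shows, and that the proteins significant by MS go on to enrichment analysis. No later step uses a finding of similarity, and no equivalence claim is planned. This stands. A reader might infer that a genuine signature would be lost because PCA fails to show it, but the documents do not support that. The t test, however, answers a question about each protein. The global statement remains with the PCA.

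**The simulations are assumed.** A reader might also infer that real differences will usually be taken for similarity. The protocol gives no effect size, no share of altered proteins and no variance structure, and the range in step 2 supports no such frequency.

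**This is a pilot, and reading a PCA plot is analysis-plan detail.** The number of components and similar details can be left to an analysis plan. The point here is what 6.2.2.7 itself states: the purpose it gives to the PCA.

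**The permutation test is no cure.** Respecting the matching costs power, and losing one of six pairs puts 0.05 out of reach. Twelve is a maximum, so this can happen. The objection stands, and it is why the reporting rule matters more than the test.

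**Section 3.3.** One secondary outcome seeks a signature "which signifies a distinct biological process that is absent in the control group". A reader might infer a planned count of controls without the process. The text describes a hoped-for result and not a per-donor yes/no rule, so binomial bounds on zero out of n answer a question that the protocol does not ask.

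**Conclusion.** The point holds in a limited form. Section 6.2.2.7 gives an unlabelled method without a criterion the task of saying whether the two proteomes are similar, and lack of separation among at most 12 donors cannot carry that conclusion. The effect is confined to the global statement of similarity or distinction, because per-protein discovery proceeds independently.

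Its size cannot be fixed from the document. At an assumed 6:6 split, separation of truly different groups on PC1-PC2 ran from about 2% to 100% of runs. The risk is real when donor, line or batch factors carry a large share of the variance, and small when they do not. That PCA ignores the label and that non-separation does not show similarity do not depend on these assumptions. The miss rates do.

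**What to change.** In section 6.2.2.7:

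1. Describe the PCA as exploratory and for quality control, and drop the task of determining similarity.
2. Base the global statement on a label-permutation test of a summary of the per-protein statistics, such as the mean F statistic. Permute within matched sets if enough complete sets remain for p below 0.05 to be attainable (with pairs, at least six). State in advance what is done otherwise, for example unrestricted permutation reported as ignoring the matching.
3. State that non-separation on the PCA, or a non-significant global or per-protein result, will be reported as inconclusive and not as similarity. Give estimated differences with 95% confidence intervals.

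Optionally, reword the secondary outcome in 3.3 so that it speaks of a difference from the control group and not of absence.

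The cost is a few lines of R and some wording, with no extra samples. The downside is that more global statements will read as inconclusive, and the p-value is coarse under within-set permutation. The test also cannot separate cardiotoxicity from reprogramming method or batch if these are unbalanced between the groups.

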3.5 RECRUITMENT

3.5.1 Participant identification

Potential participants will be identified by the clinical co-investigators, as named on page 8 of this document, at LHCH. Identification of potential participants will be based on ejection fraction measurements as determined by the results of a retrospective 3D echocardiogram. Patients who have been referred to LHCH cardio-oncology clinic with suspected doxorubicin-induced cardiotoxicity will have received a 3D echocardiogram and blood-based biomarker test at the time of their outpatient appointment and either been diagnosed with cardiotoxicity or discharged back to their referring oncologist with negative test results. LHCH will approach those who fit the inclusion criteria from this selection of patients to be involved in the study. Once eligible cardiotoxicity participants have been identified at LHCH, non-cardiotoxicity subjects will be identified based on their retrospective test

Version 2.24. Date: 1547/095/2022; IRAS:

Page 22 of 44

results and matched to the cardiotoxicity subjects on tumour type, age, and treatment regime (including dosage and time frame). Non-cardiotoxicity subjects will be approached to take part as a control cohort by one of the named clinical co-investigators.

Eligible participants will be given basic information about the study by the co-investigator either during their outpatient appointment, over the phone, or by an invitation letter sent in the post. Patients who are interested in finding out more about the study will be given a Patient Information Sheet and the option to leave their telephone number for the clinical team to make contact, or to contact the clinical team themselves using the contact information given on the PIS.

Participants will not be recruited through Patient Identification Centres, disease registers, or through media advertising such as posters, leaflets, adverts, or websites. Participants will not receive any payment for participation in this study.

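### The per-protein t test between cases and controls reads as a two-sample test that makes no use of the matching, and it estimates each protein's variance alone from about 10 degrees of freedom

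*Protocol*

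**What the plan says.** Section 3.5.1 identifies the cardiotoxicity participants first and then looks for controls, who are to be "matched to the cardiotoxicity subjects on tumour type, age, and treatment regime", with dosage and time frame counted as part of the regime. The Figure 1 legend in section 3.6.1 repeats this: "Non-cardiotoxic patients will be matched to the cardiotoxic patients on tumour type, treatment regime and approximate age". For late-onset cases it adds that the control must have been free of cardiotoxicity at the same point. The readable text gives no matching ratio, and the figure itself is not shown.

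The size is capped: "The maximum sample size for this pilot study at this stage will be 12 participants in total across all experimental groups".

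The aim in section 6.2.2.7 is stated as "To generate quantitative data on the whole proteome of doxorubicin-treated cardiomyocytes". The inference is then fixed as a t test, two-sided, and the section says that this "test will be carried out using the R computational environment to determine the statistical significance of differences in protein expression between cardiotoxicity and non-cardiotoxicity samples". Neither paired nor unpaired is written, and no pair, set or block is mentioned. Proteins found significant go on, after validation, to enrichment analysis.

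No other named test compares cases with controls. The Mann-Whitney and Kruskal-Wallis tests in section 6.2.2.4 compare early with late cell passages and individual subjects with each other. Section 6.2.2.8 names no test.

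**The concern.** The design spends recruitment effort on making controls resemble cases, and the one named case-control test does not take that up. If members of a matched set resemble each other in protein expression, the variation they share cancels from the case-control difference but stays in a two-sample standard error.

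Separately, a t test run protein by protein estimates each variance from 12 - 2 = 10 degrees of freedom at most, although the whole proteome is available to stabilise those estimates.

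With no more than 12 donors, precision is scarce. The output of this test decides which proteins enter the pathway analysis, and so it bears on the secondary outcomes about a doxorubicin signature and candidate biomarkers.

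**Working it through.** **Inputs.** From the protocol: at most 12 donors, a two-tailed t test, whole-proteome data. The protocol gives no alpha, power, effect size, SD or within-set correlation, and it bases the sample size on pilot status and feasibility, so there is no stated figure to reproduce. Assumed: six 1:1 pairs, SD = 1, nominal two-sided alpha 0.05, within-pair correlation r varied.

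**1. Standard error and size of a two-sample test on matched data.** With n pairs, the true variance of the mean difference is 2(1 - r)/n. The two-sample test estimates it as 2/n. The standard error is therefore overstated by 1/sqrt(1 - r):

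- r = 0.3: 1/sqrt(0.7) = 1.20
- r = 0.5: 1/sqrt(0.5) = 1.41

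Simulated true size at nominal 5% (300,000 replicates per value): 0.050 (r = 0), 0.041 (0.1), 0.032 (0.2), 0.025 (0.3), 0.013 (0.5), 0.004 (0.7).

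**2. A plain paired t test is not automatically better.** With six pairs the degrees of freedom fall from 10 to 5, and the critical value rises from 2.228 to 2.571. The paired interval is narrower only if r exceeds 1 - (2.228/2.571)^2 = 0.25. With four pairs the break-even is 0.41, and with three it is 0.58. Power at a 1.5 SD difference, alpha 0.05:

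| r | two-sample | paired |
|---|---|---|
| 0 | 0.65 | 0.55 |
| 0.25 | 0.67 | 0.67 |
| 0.5 | 0.69 | 0.83 |

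Stricter thresholds make it worse. At alpha 0.001 the interval break-even is about 0.55; at 2 SD and r = 0.3, power is 0.23 two-sample against 0.15 paired.

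**3. Moderated models across the proteome.** Assumptions: 3,000 independent proteins, 10% (300) truly different by 2 median SD, variances spread as inverse chi-square with 4 degrees of freedom, Benjamini-Hochberg at 5%, the same r for every protein. Power:

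| r | two-sample t | plain paired t | moderated, set as block |
|---|---|---|---|
| 0 | 0.40-0.42 | 0.06 | 0.50-0.51 |
| 0.2 | 0.39-0.40 | 0.14 | 0.62 |
| 0.4 | 0.39-0.40 | 0.32-0.33 | 0.75 |
| 0.5 | 0.39 | 0.44 | 0.82 |

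Ranges cover repeated simulations. Variance moderation without any block gives about 0.50. So at r = 0.4 the gain from about 0.40 to 0.75 splits into about 0.10 from moderation and 0.25 from blocking. At r = 0 all of it is moderation. Under these assumptions the false discovery rate of the blocked model was 0.039 to 0.050.

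**4. Where the blocked model can fail.** It estimates one correlation for all proteins. With half the proteins at r = 0 and half at r = 0.8, its false discovery rate was about 10%, against 2.3% for the two-sample test. Under a milder spread it was about 6%. A moderated model with set as a fixed effect stayed at or below 5%.

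**The case against.** The strongest reply is that the protocol never writes unpaired, and that pairing, blocking and moderation are details an analysis plan may settle. It stands in part: reading the test as two-sample is an inference. But the protocol did not leave the method open. It fixes the test, its sidedness, the two groups and the software, and groups of samples compared by a t test are ordinarily read as two-sample. If a paired test was meant, step 2 shows that this would often be a poor choice too.

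A second reply concerns the matching. Group-level matching also fits the text; no ratio is stated; and 12 is a maximum spread over early- and late-onset groups. This stands, and six pairs is only an assumption.

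A third is that r is unknown and may be small: the donors are unrelated, and the measurement is made on cardiomyocytes differentiated from reprogrammed blood cells. This also stands. At r = 0, ignoring the sets costs nothing.

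A reader might therefore infer that the test certainly discards one-to-one matching, that its error bars are too wide, and that real protein differences will be missed. The documents do not support that. They give neither the ratio nor r. Nor does section 6.2.2.7 state a multiplicity rule, so the power figures at 5% false discovery rate are not the protocol's own operating point. At unadjusted p < 0.05 and r = 0.4, the two-sample test in the same simulation already finds about 80% of the true proteins (blocked model 92%), with about 49 false positives against 134. There the conservatism reduces false leads.

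Finally, this is a pilot whose primary outcome is producing usable cells, and selected proteins are checked by Western blot. That limits the stakes without making the test efficient.

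**Conclusion.** The point holds in a limited form. Section 6.2.2.7 fixes a per-protein t test that reads as two-sample and does not use the matching described in sections 3.5.1 and 3.6.1. If matched donors are positively correlated, the test is conservative, with true size about 1.3% at nominal 5% for r = 0.5 and six 1:1 pairs. That is a loss of efficiency, not of validity.

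The variance part does not depend on r: moderation alone lifts power from about 0.40 to about 0.50 in the simulated setting. Blocking lifts it further, to about 0.62 at r = 0.2 and 0.75 at r = 0.4. All these figures rest on the assumed number of pairs, proteins, effect size, variance spread and 5% false discovery rate. The direction is firmer than the size: the blocked, moderated model had more power than the two-sample test at every r tried, including zero. The change is worth making.

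**What to change.** - In section 3.6.1, state the matching ratio and whether matching is individual.
- Record matched-set membership for each cell line at recruitment.
- In section 6.2.2.7, replace the t test by a linear model on log2 protein ratios, with case status as the effect, matched set as a block with one correlation estimated across proteins, and empirical Bayes variance moderation (for example limma with duplicateCorrelation, in R as already planned). A block term also accommodates ratios other than 1:1.
- State the error-rate threshold that defines a significant protein.
- Report a moderated model with set as a fixed effect as a sensitivity check, because the single common correlation can push the false discovery rate to about 6% to 10% when correlation differs strongly between proteins.
- Do not substitute a plain unmoderated paired t test. Under false discovery rate control it loses to the two-sample test until r is about 0.4 to 0.5.

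Cost: a few sentences of protocol wording, a standard R routine and one extra recorded variable. No new samples are needed.

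### Proteins are selected from a whole-proteome comparison by a per-protein t test and passed to pathway enrichment with no stated control of error across proteins

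*Protocol*

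**What the plan says.** Section 6.2.2.7 sets out a chain of four steps.

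- **Scope:** "To generate quantitative data on the whole proteome of doxorubicin-treated cardiomyocytes, cardiomyocytes from all experimental groups will be subjected to iTRAQ-based MS".
- **Test:** after a principal component analysis, the two cohorts are compared with a two-tailed t test in R. Its stated purpose is "to determine the statistical significance of differences in protein expression between cardiotoxicity and non-cardiotoxicity samples". The section does not say whether the test is paired, and it gives no threshold.
- **Check:** Western blots are to "verify the differential protein expression of a select number of identified proteins", compared semi-quantitatively.
- **Selection and use:** the rule for going forward picks out "proteins which are found to have a statistically significant higher or lower level of expression by MS in the control samples". Those proteins are the input to a pathway enrichment analysis.

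On numbers, section 3.6.1 states: "The maximum sample size for this pilot study at this stage will be 12 participants in total across all experimental groups". The split between cases and controls is not in the text (Figure 1 is not reproduced in the copy reviewed). The same section says: "Non-cardiotoxic patients will be matched to the cardiotoxic patients on tumour type, treatment regime and approximate age". No FDR, family-wise adjustment, permutation method or fold-change filter appears anywhere in the protocol.

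**The concern.** The selection wording works protein by protein, and the family of tests is the whole proteome. A per-test significance rule then produces a list whose length is driven partly by how many proteins are quantified. Enrichment takes that list as input and reports pathways as involved in cardiotoxicity.

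Section 3.3 makes a doxorubicin-specific signature a secondary outcome, and section 3.6.1 says the preliminary data are meant to support further funding applications. If a large part of the list is chance, the pathways carried into the next study may be chance as well, and nothing in the described procedure would show it.

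This goes beyond detail that a protocol may leave open. Section 6.2.2.7 itself fixes the test, the selection rule and the use made of the result.

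**Working it through.** The protocol gives no power, threshold, protein count or error rate for this comparison, so there is no figure of its own to reproduce.

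**Inputs**

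- From the protocol: two-tailed t test; whole-proteome scope; at most 12 donors.
- Assumed: threshold α = 0.05 per protein; m = 1,000 to 6,000 quantified proteins; 6 v 6 donors, with 8 v 4 as a sensitivity check; true standardised difference d = 0.8 to 3; share π of proteins that truly differ, 0 to 30%.

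**1. Expected false positives if nothing differs** = α × m.

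- m = 1,000: 0.05 × 1,000 = 50
- m = 3,000: 0.05 × 3,000 = 150
- m = 6,000: 0.05 × 6,000 = 300

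Correlation between proteins does not change these expectations.

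**2. Power per protein** (unpaired test, noncentral t, 10 degrees of freedom, noncentrality d × √(6×6/12)): 24% at d = 0.8, 35% at d = 1, 65% at d = 1.5, 88% at d = 2, and over 99% at d = 3.

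**3. Expected false share of the selected list** = α(1 − π) / [α(1 − π) + power × π]. At d = 1.5:

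- π = 2%: 0.049 / (0.049 + 0.013) = 79%
- π = 5%: 0.0475 / (0.0475 + 0.0325) = 59%
- π = 10%: 0.045 / (0.045 + 0.065) = 41%

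An 8 v 4 split gives 80%, 61% and 43%.

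**4. Where false positives stop being the majority.** Setting the share to one half gives π = α / (α + power).

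| d | Power (6 v 6) | Majority false when π is below |
|---|---|---|
| 0.8 | 24% | about 17% |
| 1 | 35% | about 13% |
| 1.5 | 65% | about 7% |
| 2 | 88% | about 5% |

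At π = 20% the false share is 17% to 45% over d = 3 to 0.8, and at π = 30% it is 10% to 33%.

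**5. Effect of Benjamini-Hochberg at 5%** (simulation, m = 3,000, 6 v 6, independent proteins, 100 replicates):

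| π | d | Selected at 0.05, no adjustment (false share) | Selected by Benjamini-Hochberg (FDR) |
|---|---|---|---|
| 0 | – | about 150 (all false) | about 0.1 |
| 5% | 1.5 | about 240 (about 60%) | about 2 (5.7%) |
| 5% | 2 | about 274 (52%) | about 22 (4.5%) |
| 10% | 2 | about 396 (34%) | about 93 (4.4%) |

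Bonferroni at 0.05/3,000 would leave power of only 1.6% at d = 2, so family-wise control is not a sensible choice here.

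**6. Does the Western blot help?** Only some proteins are blotted, while the enrichment input is defined by significance in the mass spectrometry data. No step removes the unblotted proteins, so the blot does not change the list.

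**The case against.** **The absence of adjustment is read from silence.** The section does not say that raw p-values will be used, and a statistical analysis plan, if there is one, could add a threshold and a correction. That stands as a limit on the claim: the protocol states no error control, which is not the same as ruling it out. It does not dispose of the point, because the protocol already fixes the test, the selection rule and the downstream use.

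**The size depends on assumptions.** This also stands. A reader might infer that most of the enrichment input will be false. The documents do not support that as a general statement. With 20% or more of proteins truly different, false positives are the minority at every effect size examined.

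**This is a pilot.** The primary outcome in section 3.3 is the generation of usable cardiomyocytes, and the molecular signature is secondary. That argues for FDR rather than family-wise control, and perhaps for a lenient level. It does not justify having no stated level, since the list is used to name pathways.

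**Stronger readings that the text does not support:**

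- That the t test ignores the matching. Paired or unpaired is not stated, and a two-tailed t test can be either.
- That early-onset and late-onset groups are pooled. The section names a two-way comparison but also refers to all experimental groups, and does not say whether one test or several are meant.
- That the blots re-measure the same cells. The preparation to be blotted is not specified.
- That the t-test list alone defines the candidate biomarkers. Aim 3 (section 2.1.3) describes other routes through cells, media and patient blood.

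**Conclusion.** The point holds as a weakness in the rule that section 6.2.2.7 sets. Followed as written at a conventional threshold, it sends a list to enrichment even when the groups do not differ: 50 to 300 proteins expected for 1,000 to 6,000 quantified. With 1.5 SD differences and 6 v 6 donors, 79%, 59% or 41% of the list is false at true shares of 2%, 5% or 10%, and false positives are the majority only below a true share of about 7% (about 5% at 2 SD, 13% at 1 SD). The threshold, protein count, split, effect size and true share are all assumptions. The direction of the problem does not depend on their exact values, but the word *most* does. The consequence falls on a secondary, hypothesis-generating outcome, and the rule should be changed before the proteomic data are analysed.

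**What to change.** In section 6.2.2.7, replace selection on statistical significance with a rule along these lines:

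> Protein abundances will be summarised to one log-ratio per donor. Case and control donors will be compared for every quantified protein, and proteins will be selected at a Benjamini-Hochberg FDR of [stated level] across all quantified proteins. Only these proteins will enter enrichment analysis.

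A moderated t test that accounts for the matched sets is preferable, and the text should in any case say whether the comparison is paired. As an alternative to a selected list, rank-based enrichment on all quantified proteins can be used, so that a short list does not limit the pathway analysis.

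The cost is protocol wording and standard R code, with no extra participants, samples or laboratory work. The drawback is sensitivity: with 12 donors the list will be much shorter and may be empty (about 2 proteins in the simulated case of 3,000 proteins, 5% truly different by 1.5 SD). For a screening pilot a more lenient FDR level is defensible, provided that it is stated in advance.
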